3.1.3 Prior and concurrent therapy

- 3.1.3.1 Patients may have had prior systemic therapy without constraint on the number of prior treatment regimens except:
- a) Patients may not have had $>450 \text{ mg/m}^2$ doxorubicin
 - b) Patients may not have had $>3000 \text{ cGy}$ to fields encompassing the entire pelvis
- 3.1.3.2 Patients must not be on any other systemic therapy within the following intervals before study enrollment:
- a) 1 week after stereotactic radiosurgery of the brain or comparable technology
 - b) 4 weeks after cytotoxic chemotherapy or external beam radiation therapy
 - c) 6 weeks after chemotherapy regimens including BCNU (carmustine) or mitomycin C
 - d) patients who experience melanoma progression (by RECIST 1.1 criteria) while on or after treatment with PD-1 or PDL-1 antibody may enroll on this study.

NOTE: Patients must be off PD-1/PDL-1 antibody for at least 2 weeks to assess for delayed toxicity before being enrolled and receiving INCB024360. Patients who are enrolled 2 weeks and up to 6 weeks after the last dose of PD-1/PDL-1 antibody will enroll in cohort B and receive 100mg BID of INCB024360.

Patients enrolled beyond the 6 week period after failing anti-PD-1/PDL-1 will be enrolled in cohort A. Cohort A patients will receive 300mg BID of INCB024360.

Patients must not have active grade 2 autoimmune toxicities attributed to these antibodies at study entry.

- e) 8 weeks after ipilimumab, other CTLA-4 antibody or other immunologically active antibody.

NOTE: Patients receiving prior CTLA-4, anti-PD1 antibody or other immunologic therapy must show evidence of normal pituitary function at baseline and must not have active grade 2 autoimmune toxicities attributed to these antibodies at study entry.

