Patients will receive 3 weeks of INCB024360, followed by continued INCB024360 plus 6 vaccinations with MELITAC 12.1. Patients who have disease progression while receiving anti-PD1 or anti-PDL-1 antibody treatment will be allowed to enroll and receive INCB024360 within 2-6 weeks of last antibody treatment administration. Patients enrolled within the 6 week window will be enrolled in Cohort B and administered INCB024360 orally at a dose of 100 mg twice daily continuously up to day 98 (3 months) plus vaccines. Patients who enroll in the study after confirmed disease progression on anti-PD1/PDL-1 after 6 weeks of receiving the last dose of antibody will be enrolled in Cohort A and receive 300 mg BID of INCB024360 plus vaccines.

Patients that show response at 3 months will be considered for additional INCB024360.

As a lead-in to ensure safety and tolerability of the combination of INCB024360 and MELITAC 12.1, the first 3 patients enrolled in the study will be at the dose of 300 mg bid staggering each patient's enrollment by at least 2 weeks so that the first patient will receive 2 doses of the vaccine in combination with INCB024360 before the second patient starts the combination of agents. Enrollment will be halted after the first 3 patients are enrolled to allow for observation of any toxicity before opening further enrollment. The next nine patients will receive either 300 mg bid of INCB024360 or 100 mg bid ([Table 5.1](#)). For patient safety, if a Dose Limiting Toxicity (DLT) occurs in the first three patients treated at the 300 mg BID dose level of INCB024360 + MELITAC 12.1 vaccine, the subsequent 9 patients will be treated with the dose of either 300 mg BID or 100 mg of INCB024360 + MELITAC 12.1. If two DLTs occur in the first 6 patients treated at the

300 mg dose of INCB024360 + MELITAC 12.1 the study will be stopped.

Treatment will be administered on an outpatient basis. Reported AEs and potential risks are described in [Section 7](#). Appropriate dose modifications are described in [Section 6](#). No investigational or commercial agents or therapies other than those described below may be administered with the intent to treat the patient's malignancy. The patient will be requested to maintain a medication diary of each dose of medication. The medication diary will be returned to clinic staff at the end of each course.

[Table 5.1. Agent Administration and Timing of Assessments](#)

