Cohort	INCB024360 Dosing	MELITAC 12.1 Dosing	Blood draws	Tumor biopsies including FNA
A Pts.enrolled >6 wks after failing anti- PD-1/PDL-1	300 mg po bid continuous for 98 days (3 months)	Intradermal/subcutaneous Days 21, 28, 35, 56, 77, 98 (Weeks 3, 4, 5, 8, 11, and 14)	Pretreatment day 0 and on days 21, 42, 98, and 112	Days 0, 21, 42, and (optional day 112) and (optional when coming off study including for progression)
B Pts.enrolled 2-6 wks after failing anti- PD-1/PDL-1	100 mg po bid continuous for 98 days (3 months)	Intradermal/subcutaneous Days 21, 28, 35, 56, 77, 98 (Weeks 3, 4, 5, 8, 11, and 14)	Pretreatment day 0 and on days 21, 42, 98, and 112	Days 0, 21, 42, and (optional day 112) and (optional when coming off study including for progression)

Abbreviations: bid, twice per day; FNA, fine-needle aspiration; po, orally; pre-tx, pretreatment; SC, subcutaneous

Enrollment will be staggered so that only 3 patients will initially be treated at the 300-mg bid dose in order to observe their response to the INCB024360-MELITAC 12.1 combination. After the first patient is started on INCB024360, treatment will proceed for 2 weeks before the second patient is started on INCB024360 monotherapy. Before the second patient starts the combination of INCB024360 and MELITAC 12, the first patient will have already received the second vaccination of MELITAC 12.1 in combination with INCB024360 and observed for any toxicity. The third patient will start INCB024360 monotherapy 2 weeks after patient number 2 has received the combination of INCB024360 and MELITAC 12.1 and been observed for toxicities. After the first 3 patients are treated at the 300-mg bid dose of INCB024360 in combination with the MELITAC 12.1 and found to tolerate the combination well, the dose of INCB024360 will be 300 mg BID for subsequent patients. Those patients treated with anti-PD-1/PDL1 antibody who have failed therapy and enrolled in the study 6 weeks or longer after progression of disease will be enrolled in Cohort A and receive 300 mg BID of INCB024360. Patients who fail anti-PD-1/PDL-1 therapy and enroll within 2-6 weeks of progression of disease will receive 100 mg BID in Cohort B. All other patients enrolled in the study will receive INCB024360 300 mg BID.

A total of 12 patients will be enrolled in the study. Assignment to Cohort A or B is for dose assignment only.

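### Section 5.1 sets the INCB024360 dose by two different clocks, weeks since progression and weeks since the last PD-1/PD-L1 antibody dose, so some patients qualify for both 100 mg and 300 mg BID

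*Combined protocol and SAP*

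**What the plan says.** The cohort label matters only because it fixes the dose; Section 5.1 says it has no other purpose. The dose is stated in several places.

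- **Section 3.1.3.2(d), note.** "Patients who are enrolled 2 weeks and up to 6 weeks after the last dose of PD-1/PDL-1 antibody will enroll in cohort B", at 100 mg BID. The next sentence sends patients beyond that 6-week period to Cohort A at 300 mg BID, although it words the starting point as failure of the antibody.
- **Section 5.1, text before Table 5.1.** Patients who progress while receiving antibody may start INCB024360 "within 2-6 weeks of last antibody treatment administration" and go to Cohort B. Those enrolling with confirmed progression "after 6 weeks of receiving the last dose of antibody will be enrolled in Cohort A".
- **Section 5.1, text after Table 5.1.** "Patients who fail anti-PD-1/PDL-1 therapy and enroll within 2-6 weeks of progression of disease will receive 100 mg BID in Cohort B". Patients who have failed antibody and enroll "6 weeks or longer after progression of disease will be enrolled in Cohort A", at 300 mg BID. All other patients receive 300 mg BID.
- **Schema and Table 5.1.** Both count weeks after failing antibody, which fits either clock. The Schema footnote limits the remaining 300 mg group to patients never treated with PD-1/PD-L1 antibody.
- **Section 2.4.3.** The early cohort was added so that INCB024360 could start soon after the last antibody dose, while PD-1 blockade is still active.

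**The concern.** Progression date and last-dose date need not coincide. Section 3.1.3.2 admits patients who progress "while on or after treatment with PD-1 or PDL-1 antibody may enroll on this study", so progression can come before the last dose (antibody continued past progression) or after it. When the dates differ enough, a site following the text under Table 5.1 gives a different dose from a site following the eligibility text, and both can point to current operative wording.

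Two things are at stake. The first is the dose itself: a patient with recent antibody exposure could receive three times what Section 3.1.3.2 sets, or a patient well past the window could receive a third of it. The second is the safety count. The stopping rule in Section 5.1 begins "If two DLTs occur in the first 6 patients treated at the" and continues with the 300 mg dose. Who is in that count therefore depends on the dose assigned, and Section 5.2 makes a grade 2 liver-test elevation a DLT.

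**Working it through.** The plan gives no figure to reproduce; this is a comparison of two rules.

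**Inputs.** Let L be weeks from last antibody dose to enrollment and P be weeks from progression to enrollment. Section 3.1.3.2 requires L of at least 2.

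- Last-dose rule (Section 3.1.3.2; Section 5.1 before the table): 100 mg if 2 ≤ L ≤ 6; 300 mg if L > 6.
- Progression rule (Section 5.1 after the table): 100 mg if 2 ≤ P ≤ 6; 300 mg if P ≥ 6; no cohort named if P < 2.

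The protocol gives no individual dates, so the timelines below are assumed.

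| L | P | Sequence | Last-dose rule | Progression rule |
|---|---|---|---|---|
| 4 | 4 | same date | 100 mg | 100 mg |
| 5 | 7 | last dose 2 weeks after progression | 100 mg | 300 mg |
| 3 | 7 | last dose 4 weeks after progression | 100 mg | 300 mg |
| 7 | 4 | progression 3 weeks after last dose | 300 mg | 100 mg |
| 6 | 6 | same date | 100 mg | both sentences apply |
| 3 | 1 | progression 2 weeks after last dose | 100 mg | no cohort named |

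**When the rules disagree.** Setting aside P = 6 exactly and P < 2, they disagree when L and P lie on opposite sides of 6 weeks.

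- *300 mg inside the Cohort B window* needs L ≤ 6 and P > 6. Antibody must then have continued for P − L weeks past progression, which is more than 6 − L. At L = 5 that is more than 1 week; at L = 3, more than 3 weeks.
- *100 mg outside the window* needs L > 6 and 2 ≤ P < 6, so progression came more than L − 6 weeks after the last dose. At L = 7 that is more than 1 week. This direction is less firmly documented. The earlier text of Section 5.1 speaks of progression on antibody, so for these patients the 300 mg assignment rests on the Cohort A sentence of Section 3.1.3.2, whose 6-week period refers back to the last-dose window just defined.

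**Internal overlap.** At P = 6 the Cohort A and Cohort B sentences under Table 5.1 both include the patient, so that text conflicts with itself whatever L is.

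**Size for an affected patient.** 300 / 100 = 3; per day, 2 × 300 = 600 mg against 2 × 100 = 200 mg.

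**Stopping rule.** One misassigned patient among the first 6 at 300 mg is 1/6 = 17% of the denominator, and a DLT in that patient is 1 of the 2 needed to stop. This is conditional arithmetic, not an estimate of how often it happens.

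**The case against.** The strongest reply is that the intended rule can be identified. The eligibility note, the earlier text of Section 5.1 and the rationale in Section 2.4.3 all point to the last dose; only the text under Table 5.1 departs from it. Section 4.1 has sites verify eligibility before registration, so they will have read the last-dose rule. The 2-week washout, serum chemistry at treatment visits (Section 10) and removal from therapy at grade 2 liver-test elevation (Section 6) limit the risk. This stands as mitigation, and it shows which way to correct the text. It does not settle the dose: the outlying sentences sit in the treatment plan beside the dosing table, and nothing ranks one section above another.

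Some stronger readings are tempting but not supported.

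- *A patient under 2 weeks from progression is sent to 300 mg by the sentence on all other patients.* The Schema limits that group to patients never given PD-1/PD-L1 antibody, and Section 3.1.3.2 puts a patient 2 to 6 weeks from the last dose in Cohort B. The fair statement is that the text under Table 5.1 leaves this patient without a clear cohort.
- *Misassignment undermines every stopping rule.* Section 6 closes accrual when more than 33% of accrued patients have a treatment-related DLT (1 of the first 3 is tolerated), and that rule counts the patient at either dose. Only the 300 mg rule in Section 5.1 depends on the assignment.
- *The ipilimumab experience shows the harm.* Sections 2.3.1.3 and 2.4.3 report transaminase elevations in 5 of 7 patients given INCB024360 at 300 mg BID with ipilimumab. That is a different antibody, and two of those events followed reduction to 100 mg. The protocol gives no data on INCB024360 with a PD-1 antibody.

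**Conclusion.** The contradiction is real and lies in current dosing text. It should be corrected, because following one part of Section 5.1 can give a dose threefold different from that set in Section 3.1.3.2.

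It does not affect every patient previously treated with PD-1/PD-L1 antibody. It reaches those whose two dates fall on opposite sides of 6 weeks, those exactly 6 weeks from progression, and those under 2 weeks from progression. The documents give neither the usual gap between last dose and progression nor the expected size of Cohort B, so the number affected cannot be estimated. The protocol does not say why 100 mg was chosen, so the size of any harm is also unknown. The conclusion rests on reading the 6-week limit in Section 3.1.3.2 as inclusive and its 6-week period as running from the last dose. The main example (L = 5, P = 7) needs only the Cohort B sentence of that section.

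A secondary gap: Section 5.1 states that "the first 3 patients enrolled in the study will be at the dose of 300 mg bid" without saying that they must be outside the Cohort B window. The main point does not depend on it.

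**What to change.** 1. **Section 5.1, text under Table 5.1.** Replace the two cohort sentences with: *Patients who have progressed on or after anti-PD-1/PD-L1 antibody and enroll 2 weeks up to and including 6 weeks after the last antibody dose are in Cohort B and receive 100 mg BID; those who enroll more than 6 weeks after the last antibody dose are in Cohort A and receive 300 mg BID.* This sets one clock, removes the overlap at 6 weeks and keeps the progression requirement.
2. **Same text, sentence on all other patients.** Limit it to patients never treated with PD-1/PD-L1 antibody, as the Schema does.
3. **Schema, Table 5.1 and the Cohort A sentence of Section 3.1.3.2.** Keep the failure condition and state the clock, for example: *failed anti-PD-1/PD-L1 and enrolled >6 wks (or 2–6 wks) after the last antibody dose.*
4. **Optional, lead-in in Section 5.1.** State that the first 3 patients must not be in the Cohort B window.

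Items 1 to 3 change wording only and add no patients, visits, samples or analyses. Item 4 is a new enrollment restriction: a patient 2 to 6 weeks from the last dose would have to wait until the lead-in is complete.

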1.1 Primary Objectives

Objective 1: To determine the extent to which a regimen of INCB024360 that normalizes serum Kyn/Trp ratios alters the tumor microenvironment of melanoma, including determining the number and character of tumor-infiltrating lymphocytes as determined by examination of serial biopsies with immunohistochemistry (IHC) and gene signatures

Objective 2: To determine the extent to which continued INCB024360 treatment plus the addition of the multipeptide melanoma vaccine, MELITAC 12.1, further alters the tumor microenvironment of melanoma, including determining the number and character of tumor-infiltrating lymphocytes as determined by serial biopsies evaluating IHC and gene signatures

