2.3.1.2 Clinical Study INCB024360-101

INCB024360 is currently being evaluated in an ongoing Phase I study (INCB 24360-101) conducted by Incyte Corporation in subjects with refractory solid tumors [ClinicalTrials.gov Identifier: NCT01195311]. The study has used a 3+3 dose escalation design, with doses of INCB024360 ranging from 50 mg once daily (qd) to 700 mg twice daily (bid). A total of 52 subjects have been treated: 3 initiated treatment at 50 mg qd, 4 at 50 mg bid, 3 at 100 mg bid, 6 at 300 mg bid, 11 at 400 mg bid, 5 at 500 mg bid, and 4 at 700 mg bid. In the food effect expansion cohort, 14 subjects were treated at 600 mg bid.

INCB024360 has generally been well tolerated. The most common adverse events (AEs) ($\geq 20\%$) include fatigue, nausea, decreased appetite, vomiting, constipation, abdominal pain, diarrhea, dyspnea, back pain, and cough. The most common grade 3 or 4 AEs were abdominal pain, hypokalemia, and fatigue (9.6% each). Despite 1 patient reporting a dose-limiting toxicity (DLT) of radiation pneumonitis at 300 mg bid, additional subjects were enrolled at this dose and no additional DLTs were reported. At 400 mg bid, 1 patient reported a DLT of grade 3 fatigue, with no additional DLTs at this dose level. Another patient at 400 mg bid developed asymptomatic and transient hypopituitarism after 1 cycle of therapy and was able to continue dosing with INCB024360. Among the 18 subjects treated at either 600 or 700 mg bid, no DLTs were observed. Dose escalation was completed based on preliminary pharmacokinetic and pharmacodynamic data, which demonstrated that doses of INCB024360 above 300 mg bid achieved exposures exceeding the IC_{90} determined in nonclinical models and, in pharmacodynamic assays, reached a plateau for Kyn/Trp levels and ratios. In the final cohort of 600 mg bid, the effect of food on INCB024360 absorption was evaluated. No objective responses were reported. At 2 months, stable disease was seen in 15 patients and lasted ≥ 4 months in 7 patients. The main AE reported in subjects receiving more than 2 cycles of INCB024360 has been grade 1 or 2 fatigue.

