Plasma levels of INC024360 and plasma levels of Kyn were measured in serial samples. Steady-state linear pharmacokinetics were obtained on or before day 8, and appreciable drug accumulation with increases in mean area under the curve (AUC) by 30% between analysis on day 1 and 15 was evident. The half-life was 2.3–4 hours. Pharmacodynamic correlates suggest that significant target inhibition was achieved at bid doses \geq 300 mg bid, resulting in steady-state exposures that exceeded the IC₉₀. As a pharmacodynamic effect, blood samples for tryptophan and kynurene levels show significant target inhibition with doses of 50 mg bid or greater. In patients showing elevations at baseline, \geq 300 mg bid doses normalize kynurene levels. IHC staining of 11 patients demonstrated that IDO1 tumor expression could be observed in tumor cells, infiltrating inflammatory cells, or both, in 10 out of 11 samples, and CD3+ T cells and Foxp3+ Tregs were present in all examined samples. Based on the tolerability and these pharmacokinetic and pharmacodynamic observations, a dose of 600 mg bid has been determined as the recommended Phase-II dose as monotherapy.

In recent preliminary results from a Phase 1/2 study of INC024360 combined with ipilimumab in patients with advanced melanoma data showed that in immunotherapy-naïve patients given 25 mg BID or 50 mg BID, 42% of patients demonstrated an objective response and 75% of patients demonstrated disease control by irRC.

[\[Gibney; Hamid 2014\]](#) It is therefore proposed that reducing the dose of INC024360 from 600 mg BID to 300 mg BID in all patients may help prevent adverse events and dose limiting toxicities without limiting biological effect.

In unpublished preliminary data from Incyte, kynurene concentrations and the Kyn/Trp ratio were higher in the serum of most patients compared to controls and decreased to levels below the median for normal, after treatment with inhibitor when treated with doses that exceeded the IC₉₀ (i.e., $>$ 300 mg bid [N=19 patients]) (Table 2.4).

Table 2.4. Changes in Kynurene Concentrations and Kyn/Trp Ratios

Serum Variables	Control Patients median	Cancer Patients median (range)	Post-inhibitor median (range)
All patients (N=19)			
Kynurene, μ M	2.0	2.1 (1.3–4.2)	0.97 (0.5–1.7)
Kyn/Trp ratio, nmol/ μ mol	29.9	37.4 (17.8–68.9)	18.3 (N/A)
Select patients*			
Kynurene, μ M	2.0	2.7 (2.1–4.2)	1.1 (0.5–1.7)
Kyn/Trp ratio, nmol/ μ mol	29.9	42.0 (34–69)	18.6 (8–43)

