PD-1 blockade with pembrolizumab or nivolumab has become standard first-line therapy for advanced melanoma (based on data reported in 2015); yet most patients treated with these agents will progress on therapy. Addition of IDO inhibition to these patients offers promise for improving clinical response rates, thus, a cohort has been added to allow addition of INCB024360 early after the last dose of PD-1 antibody (or PD-L1 antibody). If data from this cohort support safety and clinical activity of INCB024360 when added to patients progressing on PD-1 antibody, these data will support future study of adding INCB024360 while continuing PD-1 antibody after failure to respond. Also, biopsies obtained after progression on PD-1 antibody and after adding INCB024360 will provide insight into the role of IDO in mediating failure of PD-1 inhibition and the changes in the tumor microenvironment of adding IDO blockade while PD-1 blockade remains active.

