13.4 Stratification Factors - None

13.5 Analysis of Secondary Endpoints

- 13.5.1 To determine whether a regimen of INCB024360 that normalizes serum Kyn/Trp ratios plus MELITAC 12.1 vaccine changes the level or character of the vaccine-induced CD8+ and CD4+ specific T-cell immune responses as measured in peripheral blood, as compared to prior published experience.
- 13.5.2 To evaluate the extent to which INCB024360 plus MELITAC 12.1 vaccine alters the number and character of PBMC populations, including T and NK cells, as evaluated by multiparameter flow cytometry.
- 13.5.3 To evaluate the extent to which INCB024360 plus MELITAC 12.1 vaccine alters the PBMC transcriptome.
- 13.5.4 To assess the safety and tolerability of INCB024360 plus MELITAC 12.1 vaccine.
- 13.5.5 To obtain preliminary data on the tumor response rate of INCB024360 plus MELITAC 12.1 vaccine by ORR, time to tumor progression, and overall survival.
- 13.5.6 To associate any observed changes with the expression of IDO1 protein by IHC in tumor or tumor-infiltrating cells.

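### The undivided CD8+ analysis appears to mix 100 mg bid Cohort B patients, recently off PD-1/PD-L1 antibody, with 300 mg bid patients, so it cannot by itself support an Objective 1 statement about a Kyn/Trp-normalizing regimen

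*Combined protocol and SAP*

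**What the plan says.** **Objective.** Objective 1 (Section 1.1) asks how far a "regimen of INCB024360 that normalizes serum Kyn/Trp ratios alters the tumor microenvironment of melanoma". Objective 3 (Section 1.2) is framed around the same kind of regimen.

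**Evidence on dose.**
- Section 2.3.1.3 says, of patients elevated at baseline and after an at-least sign, "300 mg bid doses normalize kynurene levels". This is about kynurenine, not the ratio.
- Section 2.3.1.2 says doses "above 300 mg bid achieved exposures exceeding" the IC90 and reached a plateau for Kyn/Trp.
- The text introducing Table 2.4 also refers to doses above 300 mg bid (N=19).
- For lower doses, Section 2.3.1.3 reports significant target inhibition from 50 mg bid upward.

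**Cohorts.** Sections 3.1.3.2 and 5.1 give 100 mg bid to Cohort B (2-6 weeks after PD-1/PD-L1 antibody) and 300 mg bid to Cohort A and all others. Section 5.1 fixes only the first three patients at 300 mg bid and adds: "Assignment to Cohort A or B is for dose assignment only".

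**Analysis.** Section 13.2 defines one within-patient CD8+ change and refers its power to twelve patients. Section 13.4 reads "Stratification Factors - None". Section 13 defines no analysis by cohort, by dose or by achieved Kyn/Trp.

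**Purpose of Cohort B.** Section 2.4.3 begins one sentence "If data from this cohort support safety and clinical activity of" the inhibitor and says such data would support a later combination study. It also expects Cohort B biopsies to show what IDO blockade adds while PD-1 blockade is still active.

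**The concern.** The result is meant to be read as the effect of a normalizing regimen, but some of the patients behind it may be on a dose for which the documents never claim normalization. Section 2.4.3 also says PD-1/PD-L1 blockade can raise T-cell infiltration, which is what the primary endpoint measures, and Cohort B enters while that blockade is expected to be active. Using each patient as their own control removes stable differences between patients. It does not remove a difference in dose, or a PD-1 effect that changes between biopsies.

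Sections 1 and 11 make follow-on trials depend on whether substantial changes at tumor sites are seen. A flat overall change could hide an effect in patients whose ratio normalized, and a positive one could owe something to residual antibody. The question Section 2.4.3 sets for Cohort B would have no planned analysis.

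**Working it through.** **1. Size of Cohort B.** Total 12, with the first 3 at 300 mg bid (Sections 5.1, 13.3). So k, the number in Cohort B, lies between 0 and 12 − 3 = 9.

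**2. The plan's own figure.** Section 13.2 calls 12 patients adequate for an increase of about 1 SD, where the SD of the published densities is 143 per mm². It gives no test, alpha, power or within-patient correlation ρ, so no number can be reproduced. I assume a paired t-test at two-sided 5%, with SD of change = 143 × √(2(1 − ρ)). For n = 12 and a true change of 143 per mm², noncentral-t power is:

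| ρ | SD of change (per mm²) | Power |
|---|---|---|
| 0 | 202 | 61% |
| 0.25 | 175 | 73% |
| 0.5 | 143 | 88% |
| 0.75 | 101 | 99% |

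**3. Effect of mixing.** Let the 300 mg bid effect be 1 SD and the Cohort B effect f SD. The expected overall change is 143 × [(12 − k) + k·f] / 12. For k = 4, f = 0 this is 143 × 8/12 = 95 per mm². For k = 6, f = 0 it is 143 × 6/12 = 72 (71.5). Pooled power is from 200,000 simulated trials per setting; power for the 300 mg bid patients alone is exact.

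| k | ρ | Pooled, f = 0 | Pooled, f = 0.5 | Pooled, f = 1 | 300 mg bid alone (n = 12 − k) |
|---|---|---|---|---|---|
| 4 | 0.5 | 47% | 73% | 88% | 68% |
| 6 | 0.5 | 27% | 63% | 88% | 51% |
| 4 | 0 | 28% | 45% | 61% | 41% |
| 6 | 0 | 17% | 38% | 61% | 29% |

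At ρ = 0.5 the two sets have equal power when f is about 0.4 (k = 4) or one third (k = 6). Below that the 300 mg bid set has more power; above it the pooled set does.

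**4. An illustration of upward bias.** Take no effect at 300 mg bid and an assumed 2 SD rise in six Cohort B patients from residual PD-1 blockade, with ρ = 0.5. The pooled test is then significant in about 61% of runs. The 2 SD is my assumption; a waning antibody effect would push the change the other way.

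**5. Is dose a clean stand-in for normalization?** No.
- The ratio evidence is for doses above 300 mg bid, and the sentence that includes 300 mg bid is about kynurenine.
- In the selected patients of Table 2.4 the ratio after treatment ran from 8 to 43, against a control median of 29.9.
- By the table's footnote 14 of 19 had a baseline ratio above 30, leaving 19 − 14 = 5 who did not.

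Section 9.2.5 and the study calendar (Section 10) already schedule Kyn/Trp at baseline, day 21 and day 42, so normalization can be checked patient by patient.

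**6. Cohort membership.** Section 3.1.3.2 and the earlier text of Section 5.1 count the 2-6 weeks from the last antibody dose. The text after Table 5.1 counts from disease progression. One patient can fall in different cohorts under the two rules.

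**The case against.** **No pooled test is written down.** Section 9.2.1 plans descriptive statistics, Section 11 calls the objectives exploratory, and the cohort sentence could mean only that there is no separate accrual target. This stands in part: pooling is an inference from the single N, the single change and the absence of strata, and the t-test is mine. But nothing provides for separation either.

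**A reader might infer that 100 mg bid does not normalize the ratio.** The documents do not say so. They report inhibition from 50 mg bid and are silent on normalization at 100 mg bid. It is unproven, not shown to fail.

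**A reader might infer that restricting to 300 mg bid patients is better powered.** That holds only if Cohort B has little effect. At half effect the pooled set wins (73% against 68%; 63% against 51%). Nor does 300 mg bid match the above-300 evidence cleanly, so making those patients the sole primary set is a trade-off, not a correction.

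**A reader might infer that residual PD-1 antibody inflates the result.** The direction is not established. Cohort B patients have progressed on or after the antibody, and a fresh baseline biopsy is taken within 14 days before treatment, so antibody may already act at baseline and then wane.

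**A reader might infer that Cohort B toxicity would be hidden in the total.** Section 6 monitors continuously and closes accrual when more than 33% of accrued patients have a treatment-related DLT. Three such events in patients 4 to 6 would be 3/6 = 50% and would close it. Dilution needs late events.

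**Conclusion.** The point holds as one about interpretation. If Cohort B enrols anyone, the all-patient CD8+ change combines two exposures and two PD-1 backgrounds, and the plan gives no means of attributing it to the regimen Objectives 1 and 3 name. Section 2.4.3 wants to learn from Cohort B, and Section 13 has no analysis for it.

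The size depends on accrual and on an unknown effect at 100 mg bid. With k = 0 there is no problem. At ρ = 0.5, pooled power runs from 47% to 88% for k = 4 and from 27% to 88% for k = 6, against 68% and 51% for the 300 mg bid patients alone. These figures rest on an assumed test, alpha, correlation and 1 SD effect, and they do not favour either set throughout. The change should be made, but in an exploratory trial of 12 it does not undermine the design.

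**What to change.** Amend Sections 5.1, 13.2 and 13.4 as follows.

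1. Report the CD8+ change for all 12 patients, and separately for 300 mg bid and Cohort B patients.
2. Show each patient's CD8+ change against their measured day-21 Kyn/Trp.
3. Require any Objective 1 statement about a normalizing regimen to be supported by the patients whose Kyn/Trp normalized, not by the all-patient figure alone. Fix the normal limit beforehand, for the material actually assayed (the objective says serum, Section 9.2.5 ships plasma). Say how patients already within the limit at baseline are classed.
4. Tabulate DLTs and response by dose group and by prior PD-1/PD-L1 exposure.
5. Reconcile the two definitions of the 2-6 week window, since they decide cohort membership.

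The cost is wording and a few tables from data already scheduled. The drawback is that the subgroups will be small and can only be described. No dose, stopping rule or other clinical rule is proposed.
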